### Conceptual model of barriers to change.

Addressing this weakness, we and others have begun demonstrating that such affective (i.e., automatic) feeling states are the primary motivational factors driving humans to engage in physical activity. Furthermore, these motivational factors have highly transient effects, exhibiting more state than trait qualities. Our team developed the Wants and Aversions for Neuromuscular Tasks (WANT) model to explain these relationships based on Kavanaugh's model of affective motivation states determined by motive states, affective valence (pleasure/displeasure), and arousal/activation. Past models by contrast have relied exclusively on social cognitive theory (SCT) constructs (i.e., self-efficacy, outcome expectations, sociocultural traits). Therefore, we must test not only SCT constructs but also WANT model real-time states to link T1D-related barriers to physical activity (Figure 2).

In sum, our secondary objectives will address underlying psychological mechanisms of the intervention. Knowledge of these mechanisms would improve tailoring. For example, if we find an individual's lack of motivation for physical activity is predicted by having below-average starting blood glucose, a below-average blood glucose reading an hour before opportunities for physical activity would trigger a reminder for additional carbohydrates. On the other hand, if we find the predictor is *fear* of hypoglycemia, the message would provide psychological support such as cognitive behavioral therapy for fear of hypoglycemia. To generate the needed mechanistic knowledge, we have proposed the secondary aims of this study.

**Figure 2.** Hypothesized conceptual model of factors influencing physical activity behavior change. Dotted lines indicate alternative hypothesis that T1D-related barriers directly impact physical activity without mediation by motivation states.

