# STUDY PROTOCOL

# **Social Behavioral Template**

#### 6.1.1 Data Collection

#### STUDY DESIGN OVERVIEW

The study is a single-group longitudinal study with periods of familiarization with devices, intervention using devices and mobile app, and maintenance follow-up (Figure 4). The primary aim is observing the intervention for feasibility, acceptability, and mathematical robustness. The secondary aim is observing psychological and biometric outcomes through assessments (Table 2) which are completed 1x/weekly during the entire study to test long-term effects (hypothesis 2-1-2 & 2-2-1) and 5x/daily during maintenance follow-up to test momentary effects (hypothesis 2-1-1 & 2-2-2). The secondary aim also includes an interview at the end of the study (hypothesis 2-3).

**Figure 4.** Individual participant timeline. Blue indicates measures for primary aims and red indicates measures for secondary aims.

Table 2. Surveys used for secondary aims. Appendix has instruments for dependent variable (#2a,2b), independent

variables fear of hypoglycemia (#3a, 3b), exercise self	-efficacy (#4), exercise self-regulation (#	
valence (#6), daily intention and competing demands  PHASE	Momentary	Weekly
	(Hypotheses 2-1-1, 2-2-2) (Timepoints T1-T2)	(Hypotheses 2-1-2, 2-2-1) (Timepoints T0-T2)
ASSESSMENT SCHEDULE	5x daily at random times within 3hr bins under ambulatory conditions of daily living	Weekly in controlled setting (tele-video in quiet room)
DEPENDENT VARIABLE††		
Cravings for Rest and Volitional Energy Expenditure (CRAVE) survey of motivation states for physical activity*	Score of 1-item want "right now" and 1-item aversion "right now"	Score of 5-item want "past week" and 5-item aversion "past week"
INDEPENDENT VARIABLES		
Fear of hypoglycemia†	Score of 1-item "next 3 hours" version	Weekly score of 18-item "past week" version
Fear of hyperglycemia ††	Score of 1-item "next 3 hours" version	Weekly score of 24-item "past week" version
Blood glucose metrics‡	Past 3 hours averages and slope	Weekly averages
Exercise self-efficacy 	N/A	Weekly score of 9-item "past week" version
Exercise self-regulation 	N/A	Weekly score 15-item "past week" version
COVARIATES		
Non-T1D-related affective valence states previously associated with CRAVE score (pleasure/displeasure  , activation/arousal  ).§	Score of 1-item "right now" versions	Weekly score of 1-item "past week" versions
Day of week, time of day	Timestamp	N/A

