Weather (temperature, humidity, windchill for GPS location by National Weather Service)	Momentary value	Weekly averages

August 13, 2024

Version #7

Physical Activity Daily Intention  multiple choices (exercise in morning, occupational activity, etc  )	Daily state	Weekly frequencies
Competing Demands "How busy is today's schedule?"82	Daily state	Weekly averages
Illness "Were you sick yesterday?"	Daily state	Weekly frequency
Sleep (total, waketime after sleep onset)**	Daily state	Weekly averages

††Dependent variable for aim 2-1. For aim 2-2, this is an independent variable and the dependent variable is Actigraph-measured physical activity. \*Validated in ref for 5-item versions and ref for 1-item versions. †1-item is emerging new instrument and 18-item widely validated ( $\alpha$ =.89). ††1-item parallels fear of hypoglycemia item one row up, and 24-item is validated ( $\alpha$ =.92). ‡Assessed by Dexcom G6 continuous glucose monitor (mean error 9%-10%). Quantified as consensus metrics (Coefficient of variation, mean, time in target range [70-180 mg/dL], time above range, time below range i.e. hypoglycemic). §.41-.88 convergent validity. ||assess at wakeup and apply to all timepoints that day. \*\*Assessed by Actigraph GT9X. Each 60-s epoch will be scored as wake or sleep (Sadeh's algorithm).

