#### 7.2.1 Secondary Objective Analyses (if applicable)

All statistical models for secondary objectives 1 and 2 will estimate intraclass correlation coefficient (ICC) to assess the proportion of variance explained by participant ID.

Secondary Objective 1 (STATISTICAL, MULTILEVEL MODELING). Examine whether recognized T1D-related physical activity barriers (fear of hypoglycemia, glycemic variation) predict momentary and long-term variation in motivation states for physical activity

**Hypothesis 2-1-1. Momentary predictors of motivation states.** We will develop two multilevel models for the dependent variables of want and aversion for physical activity (CRAVE 2-item "right now") respectively. The independent variables and covariates (Table 2) will be separated into momentary states for level 1, daily states for level 2, and demographics for level 3.

Hypothesis 2-1-2. Week-to-week changes in motivation states. We will develop two generalized linear mixed models for the dependent variables of want and aversion for physical activity (CRAVE 10-item "right now") respectively. A random intercept will incorporate correlations within-subject. We will include long-term assessed independent variables and covariates (Table 2, last column) along with a time categorical variable to estimate the contribution of changes coinciding with intervention (T0 to T1) and maintenance follow-up (T1 to T2).

Secondary Objective 2 (STATISTICAL, MULTILEVEL MODELING). Examine whether motivation states for physical activity predict momentary and long-term variation in physical activity behavior change, adherence, and maintenance resulting from a T1D motivational physical activity intervention.

August 13, 2024

Version #7

Hypothesis 2-2-1 – Predictors of physical activity behavior change and adherence over the intervention. We will develop a generalized linear mixed model for physical activity behavior testing WANT and SCT constructs as independent variables. A random intercept will incorporate correlation within-subject. We will include long-term assessed independent variables and covariates (Table 2, last column) along with a time categorical variable to estimate the contribution of changes from intervention (T0-T1) and maintenance follow-up (T1-T2).

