#### 7.2.3 Interim Analysis (if applicable)

The sole stopping rule will be clear evidence of harm.

There is no possibility of futility of treatment or overwhelming evidence of the benefit of treatment. This is because the present study is evaluating treatment feasibility and psychological mechanisms, but not treatment effect.

August 13, 2024 Version #7

As such, no interim analyses are planned.

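### In Hypothesis 2-2-1 the time term is described as the intervention's contribution, but the model adjusts for scores the intervention may work through, so it estimates only the residual change

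*Combined protocol and SAP*

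**What the plan says.** Section 7.2.1 plans one generalized linear mixed model of physical activity for Hypothesis 2-2-1, "testing WANT and SCT constructs as independent variables", with a random intercept per participant. Its terms are set in one sentence: "We will include long-term assessed independent variables and covariates (Table 2, last column) along with a time categorical variable". The purpose given for the time variable is the text at issue: "along with a time categorical variable to estimate the contribution of changes from intervention (T0-T1) and maintenance follow-up (T1-T2").

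The last column of Table 2 (section 6.1.1) holds weekly fear of hypo- and hyperglycemia, glucose metrics, exercise self-efficacy, exercise self-regulation, affect, weather, intention frequencies, competing demands, illness and sleep. The weekly CRAVE want and aversion scores join them as predictors. The Table 2 footnote says of CRAVE: "For aim 2-2, this is an independent variable and the dependent variable is Actigraph-measured physical activity".

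On the role of these scores, section 1.1 says "our secondary objectives will address underlying psychological mechanisms of the intervention". It also lists motivational encouragement among the components the app delivers, and Secondary Objective 2 calls the intervention motivational.

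Hypothesis 2-1-2 has a similar layout, but motivation is its outcome and its wording is softer: "time categorical variable to estimate the contribution of changes coinciding with intervention (T0 to T1"). Unadjusted estimates beside adjusted ones are promised only for Hypothesis 2-2-2.

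**The concern.** A regression coefficient answers a question that depends on what else is in the model. If the app raises motivation and motivation raises activity, a model holding motivation fixed removes that route from the time coefficient. What is left is the before-to-after change that motivation and the other adjusted scores do not explain. The 2-2-1 text describes this remainder as the contribution of changes from the intervention.

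The risk is one of interpretation. The better the plan's conceptual model holds, the smaller the time coefficient becomes, and a reader who follows the stated purpose could take a small value to mean that little changed over the intervention. As no total change is planned for this model, nothing beside it would correct that reading. The word *from* also suggests causation that a single-group comparison cannot support.

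**Working it through.** The plan states no numerical result for this term, so there is no figure to reproduce. The check traces the model terms and then applies a linear identity.

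**Which terms could be intermediates**
- Motivation (CRAVE): supported by section 1.1 and by the wording of Secondary Objective 2.
- Self-efficacy and self-regulation: plausible, because the SCT constructs are tested beside motivation as explanations of activity.
- Fear of hypoglycemia and glucose metrics: plausible, because the Synopsis names both as challenges an exercise intervention must address, and Tools 3 and 4 (section 6.1.1) feed back on glucose around exercise.
- Intention: inferred only. Table 2 lists it as a covariate.
- Weather: the app cannot change it.

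The motivation, self-efficacy, self-regulation and fear surveys are repeated weekly after the app starts (Table 1, Table 2).

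**Identity.** Let t be 0 before and 1 after, M = m₀ + a·t and Y = y₀ + c′·t + b·M. Then the total change is c = c′ + a·b. A model with time alone estimates c. A model with time and M estimates c′ = c − a·b. If a share s of the change is mediated, c′ = (1 − s)·c.

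**Illustration.** The documents give no mediated share, so s was varied from 0 to 100%. Inputs:
- c = 0.71, the pilot's d for weekly exercise minutes (section 1.2.1), used only as a scale
- b = 0.5, assumed
- 21 completers (section 7.1)
- two weeks before and two after, matching the Actigraph periods of days 8-22 and 50-64 (section 6.1.1, Mailing)
- assumed SDs: 0.6 between persons for both M and Y, and within persons 0.8 for M and 0.7 for Y

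For s = 0.5, a = 0.5 × 0.71 / 0.5 = 0.71, so a·b = 0.355 and c′ = 0.71 − 0.355 = 0.355.

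Mean time coefficients from random-intercept fits (200 replicates at n = 21, 20 replicates at n = 400; some fits gave convergence or boundary warnings):

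| Share mediated | c′ by formula | Adjusted, n = 21 | Time-only, n = 21 | Adjusted, n = 400 | Time-only, n = 400 |
|---|---|---|---|---|---|
| 0% | 0.71 | 0.731 | 0.737 | 0.721 | 0.718 |
| 25% | 0.532 | 0.540 | 0.728 | 0.530 | 0.713 |
| 50% | 0.355 | 0.364 | 0.698 | 0.352 | 0.703 |
| 75% | 0.177 | 0.169 | 0.717 | 0.189 | 0.718 |
| 100% | 0 | −0.013 | 0.716 | 0.004 | 0.700 |

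The adjusted coefficient follows c′, and the time-only coefficient stays near 0.71 at every share.

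**What the contrast covers.** Table 1 runs the app from Visit 4 (day 22) to Visit 8 (day 50). The Actigraph is worn on days 8-22 and 50-64. For the aim 2-2 outcome, the available comparison is therefore familiarization against the two weeks after the app period. No Actigraph data are scheduled while the app is in use.

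**The case against.** The strongest reply is that the plan does not seek a treatment effect. Section 7.2.3 says "the present study is evaluating treatment feasibility and psychological mechanisms, but not treatment effect", and section 7.1 limits 2-1-2 and 2-2-1 to effect sizes without a claim of power. For whether motivation states predict activity, adjusting for time and the other scores is reasonable, and keeping time in the model protects the psychological coefficients from shared trends across phases. *Contribution* can also be read as contribution given the other terms. A block f² needs fits with and without the block, so some nested fitting is already implied.

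Most of this stands, and it limits the point. A reader might infer that full mediation would make the plan reach the wrong mechanistic conclusion. The documents do not support that. Secondary Objective 2 is answered by the WANT and SCT coefficients and their f², and full mediation would show as a signal there with little residual time effect, which agrees with the conceptual model. Nor does the plan say that a near-zero time term will be reported as no contribution.

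A reader might also extend the fault in full to 2-1-2. There motivation is the outcome and is not adjusted for, and the text already says *coinciding with*.

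What the reply leaves unanswered is the stated purpose of the time term in 2-2-1. Disclaiming a treatment effect in one section does not fit with assigning a coefficient to changes from the intervention in another. Nested fits for f² do not by themselves give a time-only base model or a reported total change.

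**Conclusion.** The concern holds for Hypothesis 2-2-1 as a mismatch between what the time term is said to estimate and what its model delivers. The coefficient is the change left after adjustment for motivation and other weekly scores. The error is confined to reading it as the intervention's contribution.

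The size in this trial is unknown. The proportional rule assumes a linear model with an identity link, scores measured without error, no unmeasured common cause of the scores and activity, and direct and mediated parts of the same sign. The plan names no link for its generalized model. The simulation also uses one before/after term where the plan has a categorical time variable, so its figures show the direction and do not forecast the result.

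In 2-1-2 the issue is smaller: only paths through fear, glucose metrics, self-efficacy, self-regulation and intention are removed.

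Even a time-only estimate would be an uncontrolled before-to-after change and should not be presented as an effect of the app. The practical weight is modest, since this is an unpowered secondary analysis, but the correction is cheap and changes what the coefficient can be said to show.

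**What to change.** 1. For 2-2-1, first fit time, the random intercept and only covariates the app cannot change, such as weather. Report that time effect as the total uncontrolled pre-post change.
2. Then add the WANT and SCT blocks. Report the change in the time coefficient beside each block's f², and label the adjusted time term *residual*.
3. In the 2-2-1 text, replace *from intervention* with *coinciding with intervention*.
4. For Actigraph outcomes, state that the contrast is days 8-22 against days 50-64, after the app period.
5. For 2-1-2, add the same time-only model as a lesser item. Its wording can stay.

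The cost is one extra model per outcome and a few lines of SAP text. No new data are needed, and the planned adjusted model is kept.

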### 7.2.2 Analysis of Subject Characteristics (if applicable)

Demographics (age, sex, gender, race, ethnicity, household income, education level, public vs private insurance, duration of T1D), descriptive characteristics (HbA1c, height, weight, insulin regimen, total daily insulin dose), and derived indices (body mass index defined as weight divided by height squared, total daily insulin dose per kg body weight) will be tabulated. Categorical variables will be reported as proportions, continuous variables will be reported as mean±standard deviation if normally distributed or median (25th %'ile, 75th %'ile) if non-normally distributed.

#### 7.2.3 Interim Analysis (if applicable)

The sole stopping rule will be clear evidence of harm.

There is no possibility of futility of treatment or overwhelming evidence of the benefit of treatment. This is because the present study is evaluating treatment feasibility and psychological mechanisms, but not treatment effect.

August 13, 2024 Version #7

As such, no interim analyses are planned.

#### 7.3 Data Relevance

The primary research question is whether a data-driven exercise intervention for T1D is feasible, acceptable, and mathematically robust. The data from this study will include provide performance metrics of the intervention on all these points.

The secondary research question is to determine mechanisms underlying the link between T1D-related barriers (glycemic stability, fear of hypoglycemia) and physical activity. The data from this study will include continuous biometric and survey data that measure these\ constructs, so that their relationship can be assessed.

# 7.4 Data Coding

All data will be coded by anonymous participant ID numbers. For web applications participants do not use in their routine care (Fitbit, GlucoseZone) staff will guide and verify that participants do not enter personal details for their username or email address, but rather their anonymous number and email address that is created and assigned by the study team (e.g., [contact]).

For electronic medical records, identifiers will be redacted prior to saving a screenshot.

During analysis, race and ethnicity will be assigned numerical codes and combined as needed (e.g., white Hispanic).

#### 7.5 Data Analysis Tools

Statistical analysis will utilize SAS (Cary, NC). Machine learning will utilize Python. Qualitative analysis will use NVivo.

#### 7.6 Data Monitoring

#### **Data Collection Forms**

Continuous glucose monitoring data will be monitored every 2 weeks through the Dexcom application programing interface, and mobile diaries will be monitored daily through the GlucoseZone application programming interface. This monitoring will include audits for completeness. Other biosensors that continuously sync with their web application programming interface (Fitbit, insulin devices) will be monitored every 2 weeks through the relevant application programming interface. Actigraph watch data will be audited for completeness when the device is downloaded after each 2-week assessment period. [name] will also perform quarterly audits for conformance with source document completion.

#### Data Integrity and Protection of Databases

Databases will be exported quarterly from REDCap, Ilumivu, Qualtrics, and Actigraph Actilife onto Yale University secure servers and audited for completeness and aberrant values using

August 13, 2024 Version #7

frequency statistics. Datasets from biosensors will be checked in on REDCap checklists as they are downloaded, and the checklists will be audited quarterly. Original reports of all biosensor downloads will be retained for verification and further data analysis.

### 7.7 Handling of Missing Data

Missing patterns will be screened for whether the missingness is associated with predictors under examination and previous values (i.e., Missing at Random). Informed by this screening we have several options for final models including Rubin's multiple imputation method and Monte Carlo Markov Chain estimation.

# 8 Data/Specimen Handling and Record Keeping

#### 8.1 Subject Data Confidentiality

Participant confidentiality and privacy is strictly held in confidence by the participating investigators, their staff, and the sponsor(s)/funding agency. Therefore, the study protocol, documentation, data, and all other information generated will be held in strict confidence. While there is a possibility of a security breach compromising subject confidentiality, several steps will be taken to safeguard the confidentiality of subjects and their data as detailed below.

All research activities will be conducted in as private a setting as possible.

All research data collected outside of the mobile applications will be assigned a study participant number and that number will only identify participants in digital databases on REDCap or Actigraph Actilife. Audio-recorded interviews and orientation sessions will be transcribed and names, places, and any other identifying information will be removed. Recordings will then be promptly destroyed. The names of participants will not be associated with these data and assessments and transcriptions will be maintained according to participant study number. A master list connecting participant study numbers to participant names will be kept on a secure server where it can only be accessed by senior level project staff. Any information published as a result of the study will be such that it will not permit identification of any participant.

All research data that is collected via the mobile applications (CGM, diary responses, exercise performance, insulin usage, carbohydrates, GPS) will be stored on the relevant web application programming interface (API) platforms (Dexcom, Fitbit, GlucoseZone), researcher dashboard (Keto-Mojo, Ilumivu, Qualtrics), or user dashboard (InPen) in accord with Yale Information Technology Services protocols (Sect 2.2, Table A1). After syncing the data, the data will be immediately deleted from the participants' biosensor devices and smartphones. Web-based application and user sessions are encrypted between the server and client browser through the use of industry standard SSL certificates. As soon as each participant completes the study protocol, their data will be immediately transferred from the API platform to Yale secure servers by secure file-protection strategies, assigned to the de-identified

#### APPROVED BY THE YALE UNIVERSITY IRB 8/14/2024

Protocol Number 2000035846

August 13, 2024 Version #7

participant study number noted in the previous paragraph, and deleted from the API platform. All data is encrypted both at rest and in transit.

Yale Information Technology Services has reviewed all devices that transmit data for the study. They have determined that the Actigraph GT9X blinded watch, Dexcom G6 CGM, Fitbit Inspire 3 smartwatch, Ilumivu mobile surveys, Qualtrics mobile surveys, InPen, and participants' own insulin pumps will not collect or transmit any HIPAA-covered health information for study purposes. They have determined that GlucoseZone in this study will collect and transmit HIPAA-covered health information, in a manner meeting the HIPAA privacy and institutional standards, including GlucoseZone's specific data use agreement with Yale University.

Right to privacy for participation in this research will be protected through alphanumeric coding of data (in place of names) and proper storage of research records, including interview transcripts and data downloaded from the web API platforms. Collected materials will be maintained via an alphanumeric reference system maintained by [name]. Participants' names will appear only on the consent form, the HIPAA authorization form, and a master list maintained on REDCap that is separate from research data. Our data collection and management procedures are fully compliant with HIPAA. Access will be limited to personnel intimately involved in the study. Electronic data will be deidentified and password protected. Only members of the study team will have access to the physical or electronic data.

Study participant research data, which is for purposes of statistical analysis and scientific reporting, will be transmitted to and stored in a password-protected OneDrive folder at the Yale School of Medicine Section of General Internal Medicine. This will not include the participant's contact or identifying information. Rather, individual participants and their research data will be identified by a unique study identification number. The study data entry and study management systems used will be secured and password protected. At the end of the study, all study databases will be de-identified and archived indefinitely at the Yale School of Medicine Section of General Internal Medicine.

Data availability: Individual deidentified participant data (including data dictionaries) will be shared. This includes individual participant data that underlie the results reported in any aspect of a published article (text, tables, figures, and appendices). Other documents that will be available include the study protocol, statistical analysis plan, informed consent form, and analytic code. The data will be available immediately following publication with no end date. Data will be shared with researchers who provide a methodologically sound proposal to achieve aims in the approved proposal. Proposals should be directed to [name] at Yale University ([contact]). To gain access, data requesters will need to sign a data access agreement. Data will also be uploaded to NIH per the NIH data sharing agreement.

Representatives of the Institutional Review Board (IRB), regulatory agencies or study sponsor/funding agency may inspect all documents and records required to be maintained by the investigator for the participants in this study. The study site will permit access to such records.

